Rationale: This modification was made to allow for some mechanistic studies to better characterize the immune responses to Sci-B-Vac™ and Engerix-B®.

Section 4.3.2 "Subject withdrawal from Investigational product' The use of a concomitant medication not allowed on study as a possible reason for withdrawal from the investigational product (after consultation with the medical monitor) is now provided as an example under "Other (specify)".

Rationale: Given the age of the population being enrolled, it is expected that some study subjects may need to be removed from the investigational product because they require a concomitant medication not permitted while on the study.

Section 5.6.1

All subjects must record their daily temperature in their diary. The condition that only subjects with a low grade fever need to record their daily temperature, has been removed.

Rationale: All subjects are required to complete all elements of the safety diary provided at each vaccination, including the daily temperature log.

6.1.2 "Check Inclusion and Exclusion Criteria" Verification of eligibility against all inclusion and exclusion criteria required prior to randomization. Prior to vaccine administration on Study Days 0, 28, and 168, the investigator or qualified designee must only verify that the subject remains eligible to be administered the vaccine and to remain on the study.

Rationale: Clarification provided that on the days of vaccine administration, subject must only be verified to be eligible to have the vaccine administered (i.e. no fever, no contraindicated medications that would preclude vaccination) and to continue on the study.

Section 6.1.10
"Recording of
Adverse Events"

Clarification is provided that the recording of solicited pain, tenderness and pruritus at the injection site and oral daily temperature is only required on the day of injection and for 6 days after the injection. Safety laboratory Visit 2 in the main study has been replaced with a telephone follow up, 7 days after the first vaccination.

Rationale: This clarification is provided to distinguish between solicited adverse events (up to 6 days post injection) and unsolicited adverse events (up to 27 days post injection) and to update the 7-day telephone follow up after the first vaccination, for consistency with Section 3.1.

xxvi | Page CONFIDENTIAL

Section 6.2.1 "Urine pregnancy test"

Clarification is provided that a confirmatory serum pregnancy test is required in the event of a positive urine pregnancy test. If the serum pregnancy test is positive, the subject will be withdrawn from the study (per section 4.3.1). If the serum pregnancy test is negative, the subject will remain in the study and continue to receive the study vaccine.

Rationale: This clarification has been added to provide clear guidance on the course of action in the event of a positive urine pregnancy test.

Section 6.2.3 "Safety laboratory evaluations"

Section 6.2.3 has been removed and replaced with new section 6.2.4.1 "Clinical laboratory sub-study".

Rationale: Baseline and Day 7 safety laboratories for the full study cohort have been replaced with a more intensive laboratory assessment in a subset of the full study cohort as part of a laboratory substudy (at select sites). Laboratory parameters in the sub-study are being assessed at V1 (Study Day 0) and 1 week after each vaccination (Study Days 7, 35, 175).

Section 6.2.4.2 –
"Optional sub study of cell-mediated immunity"

Modifications made to the text to reflect that subjects enrolled to the cell-mediated sub-study will be recruited from the clinical laboratory sub-study. Clarification is also provided in the text that these sub-studies will include 3 additional assessments (A1, A2, A3), one week after each vaccination.

Rationale: To clarify the enrollment procedures and sub-study requirements for the laboratory and cell-mediated immunity sub-studies.

6.2.5 "Biological samples, handling, analysis and storage"

Changes made to reflect new sample requirements for clinical laboratory assessments and the optional cell-mediated immunity sub-study, one week after each vaccination. Subjects in the clinical laboratory sub-study will be required to come for 3 additional visits (A1, A2, A3) and provide 4 additional blood samples (10 mL/visit) at V1 and at each additional visit (A1, A2, A3). Subjects consenting to the sub-study of cell-mediated immunity will be required to provide an additional 40mL at each of these timepoints (V1, A1, A2,A3).

Rationale: Changes made to reflect sample requirements for the main study, the clinical laboratory substudy and the sub-study of cell-mediated immunity, separately.

6.2.5 "Biological samples, handling, analysis and storage.

The sentence "A separate information and consent document will be provided" for biobanking has been removed. Potential study subjects will be provided information about biobanking and will be given the opportunity to consent to biobanking within the main study consent form.

Rationale: The clinical sites requested that the optional biobanking information and consent be included in the main consent form to reduce the number of pages to be read by potential study participants,. A lack of consent to biobanking will not preclude participation in the main study.

xxvii | Page CONFIDENTIAL

Section 6.3.1 Screening	g Addition of Urinalysis to the list of test to be done at screening, for consistency with the Appendix 2 Schedule of Events and Section 6.2.2 Screening Laboratory Evaluations.
Rationale: This addition that urinalysis at screen	n was made to ensure internal consistency within the protocol and to make sure ning was performed.
Section 6.3.2 "Vaccination visits"	Clarification is provided that urine pregnancy must not only be reviewed, but also be confirmed to be negative prior to vaccination.
Rationale: To provide of childbearing potential.	clarity on the rationale for inclusion of this pre-vaccination test in women of
Section 6.3.2 "Vaccination visits"	Clarification provided that inactivated vaccines should not be received 2 weeks prior to 2 weeks after any study vaccination and attenuated vaccines should not be received 4 weeks prior to 4 weeks after any study vaccination.
Rationale: Sentence restructured to improve clarity.	
Section: 6.3.3 "Safety follow up"	In the main study, the safety follow up will now consist of a telephone follow up call 7-days after each vaccination in the full study cohort. Laboratory assessments 1 week after each vaccination will be carried out at select sites (clinical laboratory sub-study).
	n made to reflect implementation of clinical laboratory sub-study and removal of evaluation in the full study cohort. Follow up telephone call is now done 7 days
Section 6.3.6 "Substudy additional visits"	Additional study visits required for subjects enrolled at select sites for the clinical laboratory sub-study and optional cell-mediated sub-study are defined.
Rationale: To clarify th mediated immunity sul	e additional visit requirements at select sites for the clinical laboratory and cell- b-studies.
Section 6.3.7 "End of study visit"	Clarification provided that lack of seroprotection corresponds to an anti-HBs level <10 mIU/mL and not <10 IU/mL
Rationale: Correction of	of typographical error.
Section 7.2.2 "Vital signs and vaccine reactions"	Clarification provided that 1) vital signs are recorded for 30 minutes following each vaccination, 2) recording of solicited reactions and temperature monitoring are required daily to day 6 post vaccination and 3) unsolicited adverse events are recorded for 27 days post vaccination.

xxviii | Page CONFIDENTIAL

Rationale: Clarification is provided as to the nature/intensity and duration of safety monitoring required following vaccination.

Multiple sections	Correction made from [1 mL, 10 μg HBsAg, Al(OH)₃ 0.5 mg/mL without
	thimerosal] to [1 mL, 10 μg HBsAg, Aluminum 0.5 mg/mL without thimerosal]

Rationale: Distinction provided regarding the adjuvant, aluminum hydroxide, and the amount of aluminum alone (0.5mg/mL) in the investigational product, Sci-B-Vac[™].

xxix | Page CONFIDENTIAL

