	 To demonstrate that the SPR 4 weeks after completion of the three-dose regimen of Sci-B-Vac™ is superior to a three- dose regimen of Engerix-B® in adults ≥ 45 years old i.e. the lower bound of the 95% two-sided CI of the difference between the SPR in the Sci-B-Vac™ arm minus the SPR in the Engerix-B® arm, achieved 4 weeks after the third vaccination, will be >5%.
Secondary Objectives	• To determine whether the SPR after 2 vaccinations with Sci-B-Vac™, evaluated 4 weeks and 20 weeks after the second vaccination (just prior to receiving the third vaccination), is

xviii | Page CONFIDENTIAL

	non-inferior to the SPR 4 weeks after receiving the third vaccination with Engerix-B [®] .
	 To compare the safety and reactogenicty of Sci-B-Vac[™] and Engerix-B[®].
Exploratory Objectives	• To compare the geometric mean concentration (GMC) of anti-HBs, 4 weeks after receiving the first vaccination, second vaccination and third vaccination, 20 weeks after receiving the second vaccination (just prior to receiving the third vaccination), and 24 weeks after receiving the third vaccination with Sci-B-Vac [™] or Engerix-B [®] .
	• To compare the SPR 4 weeks after receiving the first vaccination and second vaccination, 20 weeks after receiving the second vaccination (just prior to receiving the third vaccination), and 24 weeks after receiving the third vaccination with Sci-B-Vac™ or Engerix-B® on Study Days 28, 56, 168 and 336.
	• To compare the proportion of subjects who achieve anti-HBs levels \geq 100 mIU/mL, as a measure of an especially robust immune response, 4 weeks after each vaccination with Sci-B-Vac [™] or Engerix-B [®] , on Study Days 28, 56, and 196 and on Study Days 168 and 336.
	• To compare the rate of non-response (defined as the proportion of subjects not attaining anti-HBs levels \geq 10 mIU/mL) 4 weeks after receiving the third vaccination with Sci-B-Vac TM or Engerix-B [®] .
	• To assess the antibody responses against Pre-S1 and Pre-S2 at baseline, 4 weeks after each vaccination with Sci-B-Vac™ or Engerix-B®, and at day 168 and 336.
	• To compare SPR, GMC and rate of non-response in subgroups of interest (e.g. BMI>30), 4 weeks after receiving the third vaccination with Sci-B-Vac™ or Engerix-B®.
	• To compare clinical laboratory parameters relative to baseline 1 week after each vaccination with Sci-B-Vac™or Engerix-B® in a subset of subjects (at least 10% of the total number of subjects enrolled to the trial).

[figure not shown]

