1.4 Rationale for conducting the study

A series of clinical trials with Sci-B-Vac[™] conducted in adults, children and neonates over the past 2 decades have found that the currently approved three-dose regimen (administered on Study Day 0, at 4 weeks and 24 weeks) elicits very high seroprotection rates that are comparable to those elicited by second-generation vaccines, such as Engerix-B® or Recombivax-HB®.

More importantly, however, antibody responses following Sci-B-Vac[™] administration in both the previous and current formulations of Sci-B-Vac[™] are generally higher and faster following the first and second injections and may not decrease with age. These attributes suggest that Sci-B-Vac[™] may help to raise seroprotection rates in adults with poorer or delayed response to second-generation vaccines, including older adults, patients with diabetes mellitus, obese individuals, and smokers. The safety profile of Sci-B-Vac[™] is similar to second-generation vaccines, aside from being associated with a higher frequency of pain at the injection site in the earlier formulations.

The sponsor, VBI Vaccines Inc., is proposing two phase III clinical trials to generate additional safety and efficacy data for the current adult Sci-B-Vac™ formulation [1 mL, 10 µg HBsAg, aluminum hydroxide adjuvant, without thimerosal] in the adult population prior to seeking licensure in Canada, the U.S. and the E.U.

The current study is being undertaken to compare the immunogenicity and safety of a three-dose regimen of Sci-B-Vac™ to a three-dose regimen of Engerix-B® in adults.

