9.1 Sample size

The overall sample size for the study is driven by the superiority co-primary analysis in study subjects ≥ 45 years old. Assuming an SPR of 0.81 for Engerix-B® and 0.96 for Sci-B-Vac[™], a minimum of 540 subjects (270 per treatment group) provides 90% power to demonstrate superiority of SPR, assuming a 5% margin with a two-sided type 1 error of 0.05, i.e., to rule out a <5% difference in SPR based on the lower limit of the two-sided 95% confidence interval. Based on a targeted enrollment of 80% of study subjects age ≥45 years-old, an additional 180 (20%) 18-44 year old study subjects would be required, for a total of at least 680 subjects in the full study. A sample size of 680 would provide ≥ 90% power to demonstrate non-inferiority with a 5% margin if the Sci-B-Vac[™] SPR is as low as 0.88, with the same SPR for Engerix-B® (0.81), and the two-sided alpha is 0.05. A 5% margin of non-inferiority is justified by the > 90% SPR of Engerix-B® in young adults. In older adults, a 5% margin of superiority represents a clinically meaningful improvement at both the individual level and from a public health perspective, given the reduced immunogenicity of Engerix-B® in this population.

Given the desire to have robust immunogenicity estimates of SPR in the adult population following a three-dose regimen of Sci-B-Vac[™] and to guard against a better than expected SPR for Engerix-B[®] (up to 84% in subjects ≥45 years old), a total of 1,564 subjects will be enrolled to the trial. There will be targeted enrollment, with 80% (~n=1252) of the study population being ≥ 45 years old and 20% (~n=312) being 18-44 years old. This sample size will provide >90% power to establish the superiority of Sci-B-Vac[™] over Engerix-B[®] in older adults (≥45 years old) and non-inferiority in adults ≥ 18 years old, given the above statistical parameters.

Given the desire to have good representation across the spectrum of older adults, the targeted enrollment of adults \geq 45 years old (80%) will be divided equally between the 45-64 year old and \geq 65 year old strata.

Targeted enrollment by age strata will be as follows:

Age 18-44 years (20%): 312 (~ 156 per arm) Age 45-64 years (40%): 626 (~313 per arm) Age ≥ 65 years (40%): 626 (~313 per arm)

Enrollment within each stratum will be stopped once the target has been met.

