9.5 Co-Primary Objectives

9.5.1 Co-Primary Hypotheses

The two co-primary analyses will be tested in sequence, the test for superiority in the subgroup (\geq 45 year-olds) can only be conducted after non-inferiority in the overall population (\geq 18 year olds) has already been shown.

1) Non-Inferiority of Sci-B-VacTM compared to Engerix-BSM will be assessed using the PPS for the entire study population (i.e., adults \geq 18 years old). The non-inferiority margin is set at 5%. The null and alternative hypotheses are as follows;

Null Hypothesis: SPR(Sci-B-Vac[™]) –SPR(Engerix-B[®]) <= -5%

Alternative Hypothesis: SPR(Sci-B-Vac[™]) –SPR(Engerix-B[®]) > -5%

Non-inferiority will be assessed using the lower bound of the two-sided 95% confidence interval. If the lower bound is greater than -5%, Sci-B-Vac™ will be declared non-inferior to Engerix-B®, and the study will be considered a success.

2) Superiority of Sci-B-VacTM compared to Engerix-B® will be assessed using the FAS for the study population of adults \geq 45 years old. In older adults, a 5% margin of superiority represents a clinically meaningful improvement at both the individual level and from a public health perspective, given the reduced immunogenicity of Engerix-B® in this population. Therefore a superiority margin is set at 5%. The null and alternative hypotheses are as follows;

Null Hypothesis: SPR(Sci-B-Vac[™]) –SPR(Engerix-B[®]) <= 5%

Alternative Hypothesis: SPR(Sci-B-Vac[™]) –SPR(Engerix-B[®]) > 5%

Superiority will be assessed using the lower bound of the two-sided 95% confidence interval. If the lower bound is greater than 0%, Sci-B-Vac™ will be declared statistically superior to Engerix-B®. If the

lower bound is greater than 5%, Sci-B-Vac™ will be declared clinically superior to Engerix-B®, and the study will be considered a success.

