where seroprotection represent the seropositive event, trt represents treatment group and agegrp represents age group (18 - 44 years, 45 - 64 years, >=65 years).

The estimated proportion of responders (i.e., estimated responder rate) and the difference in the proportion of responders between Sci-B-VacTM and Engerix-B® will be estimated, as well as the 2-sided 95% CIs for the difference. The creation of the estimates of the proportions and difference in proportions will be completed using the process detailed below:

Statistical Analysis Plan

- 1. Use the logistic regression model to calculate:
 - a) Least squares mean estimates of the log odds of Sci-B-VacTM (Gc) and Engerix-B® (Gp), as well as their corresponding standard errors (S_C and S_P, respectively)
 - b) Standard error of the least squares mean estimate of the log odds ratio (S_R)
- 2. Compute estimates for predicted proportions using the following transformations:

$$P_C = \exp(G_C)/(1 + \exp(G_C))$$
$$P_P = \exp(G_P)/(1 + \exp(G_P))$$

The difference in proportions is then given by:

$$D = P_C - P_P$$

3. Estimate the standard error of D by:

$$S_D = sqrt[P_C^2 (1-P_C)^2 S_C^2 + P_P^2 (1-P_P)^2 S_P^2 + P_C (1-P_C) P_P (1-P_P) S_R^2 - P_C (1-P_C) P_P (1-P_P) (S_C^2 + S_P^2)]$$

Analyses of the co-primary endpoints will also be conducted and reported by key sub-groups using the sub-groups identified in Section 6.2.7.

• Sample SAS code for the subgroup analysis of binary data:

```
PROC FREQ; * specify and sub-select data set as applicable;

TABLES subgroup*trt*seroprotection/riskdiff (cl=mn); * numerical 0/1-scores identify 'event';
RUN;
```

where seroprotection represent the seropositive event, trt represents treatment group and subgroup represents subgroup defined in Section 6.2.7.

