6.3.13.4 Exploratory Objective Analyses

Analysis of all exploratory immunogenicity endpoints will be based on the PPS, unless otherwise indicated. Exploratory efficacy endpoints will be summarized and analyzed without adjustment for multiple comparisons.

Geometric mean concentration (GMC)

All statistical analyses will be performed on the logarithmically (base 10) transformed values.

Statistical Analysis Plan

Adjusted estimates of GMCs and their associated 95% CIs at Day 28, Day 56, Day 168, Day 196 and Day 336 will each be determined using an analysis of covariance (ANCOVA) model with factors for treatment, age group, and a covariate for the log transformed pre-vaccination (baseline) titer. Antibody GMCs, associated standard errors, two-sided 95% CIs and median, minimum, and maximum titer values will be determined and presented by treatment group. The median, minimum, and maximum values will be reported on the actual titer values, rather than the log scale. The difference in GMCs between the two treatment groups, and associated two-sided 95% CIs will also be presented. Imputation methods will not be used.

The above analyses will be conducted and reported for all subjects age \geq 18 years old and for subjects age \geq 45 years old. Analyses of GMC in both age cohorts will also be reported by sub-group using the sub-groups identified in Section 6.2.7. Sub-group analyses will include additional factors in the model, a factor for the sub-group of interest and the interaction between the sub-group and treatment.

Sample SAS code for ANCOVA model:

```
PROC MIXED;
CLASS treatment agegrp;
MODEL log(var) = treatment agegrp log(baseline of var);

/* var = anti-HB titer GMC */
LSMEANS treatment / DIFF CL ALPHA=0.05;
ODS OUTPUT LSMEANS=ls_means Diffs=diff;

QUIT;
RUN;
```

Sample SAS code for ANCOVA model for sub-group analyses:

```
PROC MIXED;
CLASS treatment agegrp;
MODEL log(var) = treatment agegrp log(baseline of var) subgroup subgroup*treatment;
LSMEANS treatment / DIFF CL ALPHA=0.05;
ODS OUTPUT LSMEANS=ls_means Diffs=diff;
QUIT;
RUN;
```

where var represent the anti-HBs titer, treatment represents treatment group, agegrp represents age group (18 - 44 years, 45 - 64 years, >=65 years) and subgroup represents subgroup defined in Section 6.2.7.

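### Cheap improvement: sub-group results for SPR are separate intervals per level, and the plan gives no estimate of whether the SPR difference varies between levels

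*Protocol*

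**What the plan says.** Comparing SPR, GMC and non-response in sub-groups is an exploratory objective (Protocol Summary and 2.3; SAP 1.3): "To compare SPR, GMC and rate of non-response in subgroups of interest (e.g. BMI>30), 4 weeks after receiving the third vaccination".

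For SPR, Protocol 9.5.2 and 9.6.2 repeat the co-primary and secondary analyses within each key sub-group, and 9.7 does the same for the exploratory binary endpoints. SAP 6.3.13.2 to 6.3.13.4 follow. The sample code is "TABLES subgroup*trt*seroprotection/riskdiff (cl=mn"), which prints a separate risk difference and Miettinen-Nurminen interval for each level. The only regression for SPR is a sensitivity analysis with main effects for treatment and age group (log-linear in the protocol, logistic in the SAP). The funnel plots concern center only.

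For GMC, Protocol 9.7 and SAP 6.3.13.4 add to the ANCOVA "a factor for the sub-group of interest and the interaction between the sub-group and treatment".

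SAP 6.2.7 lists 11 sub-group variables. SAP 6.3.13.4 states that exploratory endpoints carry no multiplicity adjustment.

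**The concern.** The plan puts an interaction term into the model for an exploratory endpoint (GMC) and leaves it out for the endpoint on which the trial is judged (SPR). The documents give no reason.

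The rationale in Protocol 1.4 is that the vaccine "may help to raise seroprotection rates in adults with poorer or delayed response to second-generation vaccines", naming older, diabetic and obese adults and smokers. Readers of the sub-group tables will naturally ask whether the advantage differs in these groups. Two intervals side by side do not answer that, because their widths depend on sub-group size. Protocol 9.5.1 also attaches labels to lower bounds above 0% and above 5% in adults aged 45 and over, so ready-made thresholds lie close at hand. A small sub-group that misses a threshold which its large complement clears could then be taken as evidence of a weaker effect.

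**Working it through.** **Inputs from the documents (Protocol 9.1).** "Assuming an SPR of 0.81 for Engerix-B" and 0.96 for Sci-B-Vac; "assuming a 5% margin with a two-sided type 1 error of 0.05"; 1:1 allocation; about 1,252 subjects aged 45 and over, hence 626 per arm; age strata of about 156, 313 and 313 per arm.

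**Assumed.** Sub-group shares of 5%, 8%, 15% and 30% of 626 per arm, giving 31, 50, 94 and 188. The documents fix sizes only for the age strata. No attrition. The true SPRs are the same in every level.

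**1. The plan's own figure.** Protocol 9.1 says "a minimum of 540 subjects (270 per treatment group) provides 90% power to demonstrate superiority of SPR". With variance V = 0.96×0.04 + 0.81×0.19 = 0.1923 and distance to the margin 0.15 − 0.05 = 0.10, n = (1.960 + 1.282)² × 0.1923 / 0.10² ≈ 202.1, so 203 per arm. The restricted-variance (Farrington-Manning) version gives 198. The stated 270 is not reproduced: it gives about 96–97% power, and only an unstated 25% dropout (271) comes near it. The discrepancy is conservative and does not affect this point.

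**2. Bias.** Simulated sub-group differences average 15.0 points at every size, and about half lie below the complement's estimate. Small size does not shift the estimate.

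**3. Width and misses.** The Wald half-width is 1.96 × √(0.1923/n). The chance that the Miettinen-Nurminen lower bound does not exceed a threshold comes from exact enumeration of both binomials.

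| Per arm | Half-width (points) | Lower bound fails +5 | Lower bound fails 0 |
|---|---|---|---|
| 31 | 15.4 | 75% | 50% |
| 50 | 12.2 | 59% | 31% |
| 94 | 8.9 | 37% | 7% |
| 156 | 6.9 | 16% | 0.7% |
| 188 | 6.3 | 10% | 0.2% |
| 313 | 4.9 | 1.4% | about 0% |

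**4. What a contrast would do.** For two levels, take D = (difference in level 1) − (difference in level 2), with SE = √(V/n₁ + V/n₂). With no true heterogeneity, a Wald test of D = 0 at the 5% level rejects in 6.5% of simulated trials at 31 per arm, 5.6% at 63, 5.3% at 125 and 5.2% at 188. At 19 per arm it rejects in 8.2%, so very small levels need a score or exact version. Precision is limited: for 63 versus 563 per arm, SE = √(0.1923 × (1/63 + 1/563)) = 5.8 points, a 95% CI of about ±11.4 points.

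**5. Multiplicity.** Eleven independent 5% tests give 1 − 0.95¹¹ = 43% chance of at least one false signal. The 11 variables are not independent (age appears twice), so this is a guide only.

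**6. Scale.** The planned odds ratio is (0.96/0.04)/(0.81/0.19) = 5.63. Held constant, it gives differences of 24 points at control SPR 0.68 (the 60–69 figure in Protocol 1.2), 15 at 0.81 and 6.5 at 0.92. The 0.92 is assumed; Protocol 9.1 says only above 90% in young adults. A ceiling alone can therefore make the risk difference vary with age.

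**The case against.** - **Small sub-groups will make the vaccine look weaker.** A reader might infer this, but it is not supported: the estimate is unbiased, and the printed interval shows its own width. The misreading arises only if lower bounds are compared with a threshold.
- **The plan would call a sub-group a failure.** A reader might infer this from the 0% and 5% labels. Those belong to a single test in adults aged 45 and over. No success rule is attached to any sub-group interval, and the objective is exploratory.
- **The same +5 misses apply to all adults.** They do not, because the threshold for the whole adult population is −5%. Against it, under the same rates, the miss is about 20%, 4%, 0.1% and 0% at 39, 63, 117 and 235 per arm.
- **The age strata are at serious risk.** Their planned sizes give 16% at 156 and 1.4% at 313 per arm. The 156 belongs to the 18–44 stratum, which lies outside the superiority population and has an expected control SPR above 90%, so the 16% describes a sub-group of that size at the older adults' rates.
- **The stated aims require an interaction.** The objective can be read as comparing the two vaccines within each sub-group, which the tables do. Protocol 1.4 claims improvement in poor responders, not a larger effect than elsewhere. Only Protocol 4.1 speaks of most benefit, and only for older adults.
- **GMC already does this properly.** Only in part. The model has the interaction term, but the sample code requests LS means for treatment only, and no text says that the interaction will be reported.

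These points reduce the size of the concern. The omission itself stands: no planned quantity addresses whether the SPR difference varies between levels.

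**Conclusion.** The point holds as a cheap improvement to exploratory tables. SPR and the other binary endpoints have no planned estimate of effect variation across sub-groups, although the plan models such variation for GMC. In adults aged 45 and over, an identical effect leaves the lower bound at or below +5 points often in levels of about 30 to 100 per arm, and rarely at 313. This rests on 96% versus 81% in every level, no attrition, and assumed shares for every variable other than age. The co-primary and secondary conclusions are unaffected.

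**What to change.** In SAP 6.3.13.2, 6.3.13.3 and the binary part of 6.3.13.4, for each variable in SAP 6.2.7:

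- **Two levels:** report the difference between the two SPR differences with a 95% CI.
- **Three or more levels:** report a homogeneity test on the risk differences.
- **Scale:** use the risk difference, as the plan already does, and give the odds-ratio interaction alongside. Note that age differences on the risk-difference scale may reflect a ceiling in control SPR.
- **Small levels:** use a score or exact version where a level has about 30 or fewer per arm.

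Add a short statement that the contrasts and the within-sub-group intervals are exploratory, that these intervals are not read against the 0% or 5% superiority thresholds, and that the tests are unadjusted for multiplicity (about 43% chance of at least one false signal from 11 independent tests). Report the GMC interaction estimate as well.

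The cost is a few lines of SAP text and code, mostly using quantities already computed, and extra table columns. The SAP's introduction allows amendment before database lock. Power will be low, so most contrasts will be inconclusive, and the text should say so.
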